9.2 Assessment of an Adverse Event

9.2.1 Relationship (Causality/Relatedness)

The causality assessment is the determination, according to the investigator's clinical judgment, of the existence of a reasonable possibility that the study drug (IP) caused or contributed to an adverse event.

If the investigator or delegated sub-investigator is unsure about whether or not the study drug caused or is related to the event, then the event will be handled as "related" to the study drug for reporting purposes of the trial. If the causality assessment is "unknown but not related" to the study drug, this should be clearly documented in the source documents.

9.2.2 Expectedness

Events are classified as unforeseen or unexpected if the nature, severity or frequency is not consistent with the risk information set out in Section 9.1.2 or the Product Monograph (PM) or label.

9.2.3 Seriousness

Events are classified as serious if associated with effects threatening the life or physiological functions of a participant. Refer to the definition for "Serious Adverse Events" in section 9.1.5.

9.2.4 Severity

The term "severe" is often used to describe the intensity (severity) of a specific event (e.g. mild, moderate, or severe myocardial infarction); the event itself, however, may be of relatively minor medical significance (such as severe headache). This is not the same as "serious," which is based on participant/event outcome or action criteria usually associated with events that pose a threat to a

participant's life or functioning. The terms "serious" and "severe" are not synonymous. Seriousness (not severity) serves as a guide for defining regulatory reporting obligations.

To assess the severity of an adverse event the investigators will use the following:

- the National Cancer Institute (NCI) Common Terminology Criteria for Adverse Events (CTCAE)

9.2.5 Adverse Event Recording

Investigations into potential adverse events should be done during each contact with a participant.

Investigations may be done through specific questioning and, as appropriate, by examination.

Information on all adverse events should be recorded promptly in the source document, and assessed by an investigator in a timely manner allowing sufficient time to meet required reporting timelines for SAEs and serious unexpected adverse drug reactions (SUADRs) if needed. Adverse event CRFs should be completed using source documents by a delegated research team member in a timely manner/within 15 days of site awareness. All clearly related signs, symptoms, and abnormal diagnostic procedures should be recorded in the source document, though should be grouped under one diagnosis. Each diagnosed adverse event should then be categorized in accordance with the revised NCI Common Terminology Criteria for Adverse Events (CTCAE).

The following are not considered AEs and therefore do not require recording:

- Pre-existing diseases or conditions identified and recorded at screening/baseline unless, at the discretion of the investigator, the disease or condition worsens in severity or frequency
- At the discretion of the investigator, events considered likely manifestations of the underlying disease or that commonly occur in the study population independent of study drug exposure
- Elective medical or surgical procedures.

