9.0 ASSESSMENT OF SAFETY

9.1 Definitions

9.1.1 Adverse Event

An **Adverse Event (AE)** is defined as any new event that may jeopardize the patient which the study investigator physician perceives may be directly related to the enrolment in the pilot study or to the assigned arm. Adverse events are not study related if they are related primarily to the underlying disease. All AEs are to be documented and assessed for relatedness. If related to the study drug and occurring from baseline up to one week after the final study visit, the AE will be recorded on the eCRF and coded as per the most recent edition of the Common Terminology Criteria for Adverse Events (CTCAE).

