9.1.5 Serious Adverse Event (SAE)

A serious adverse event (SAE) in the study is defined as:

- a) any event that is fatal or immediately life threatening, permanently disabling, severely incapacitating, or requires prolonged inpatient hospitalization, or
- b) any event that may jeopardize the patient and requires medical or surgical intervention to prevent one of the outcomes listed above, AND
- c) which the attending physician perceives may be directly related to enrolment in the study, or to the assigned arm.

SAEs will be considered to be study-related if the event follows a reasonable temporal sequence from the study intervention and could readily have been produced by the intervention. Adverse events are not study related if they are related primarily to the underlying disease.

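### Section 9.1.5 makes perceived relatedness part of the SAE definition and counts only prolonged hospitalization, so a short, non-life-threatening admission judged unrelated can miss SAE reporting

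*Combined protocol and SAP*

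**What the plan says.** Section 9.1.5 of the combined protocol and SAP defines an SAE by three lettered criteria.

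- Criterion (a) covers fatal, immediately life-threatening, permanently disabling and severely incapacitating events. For hospital stays it covers only an event that "requires prolonged inpatient hospitalization".
- Criterion (b) is "any event that may jeopardize the patient and requires medical or surgical intervention to prevent one of the outcomes listed above, AND".
- Criterion (c) completes the sentence: "which the attending physician perceives may be directly related to enrolment in the study, or to the assigned arm".

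A closing paragraph adds that events due mainly to the underlying disease are not study related.

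The AE rules carry similar filters. Section 9.1.1 limits an AE to a new event that the study physician "perceives may be directly related to the enrolment in the pilot study or to the assigned arm", and it makes eCRF entry conditional: "If related to the study drug and occurring from baseline up to one week after the final study visit". Section 9.2.5 then lists items under the lead-in "The following are not considered AEs and therefore do not require recording". Its first bullet removes conditions already recorded at baseline, "unless, at the discretion of the investigator, the disease or condition worsens in severity or frequency". Its second bullet removes, at the investigator's discretion, "events considered likely manifestations of the underlying disease or that commonly occur in the study population independent of study drug exposure".

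Other parts of the plan treat seriousness as separate from cause. Section 9.3.5 sends deaths and immediately life-threatening events to the sponsor within 24 hours, related or not, and all other SAEs within 72 hours whatever the relationship. Section 9.2.4 ties seriousness to the outcome of the event or the action taken. The CIOMS form in Appendix D has a box for an event that either led to or lengthened an inpatient stay.

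**The concern.** An SAE definition should select on outcome, with causality judged afterwards. Here relatedness is part of the definition, so the duty in 9.3.5 to report regardless of cause has little left to act on: an event judged unrelated may never have become an SAE. The word *prolonged* in (a) narrows the definition further, because an ordinary admission does not meet it.

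What is at stake is the consistency of the safety record. The trial is open-label, so whoever makes the relatedness judgement can know the arm. There is no DSMB (9.4), so individual SAE reports and the safety look after 20 patients (8.3) carry more of the monitoring. Two similar admissions could take different routes, one to the sponsor within days and the other to no required record.

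**Working it through.** The plan states no figure to reproduce, so the check is a reading of the sections against one another.

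**1. The event.** Take a hospital admission that is not fatal, life-threatening, permanently disabling or severely incapacitating, and that the physician attributes to something other than the study.

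**2. Does it meet 9.1.5?** The *AND* before (c) can attach to both (a) and (b), which is the natural reading, or to (b) alone.

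| Admission | (c) applies to (a) and (b) | (c) applies to (b) only |
|---|---|---|
| Prolonged | SAE only if seen as possibly related | SAE through (a); relatedness not needed |
| Not prolonged | (a) not met; through (b), only if seen as possibly related | (a) not met; through (b), only if seen as possibly related |

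The narrower reading of *AND* rescues the prolonged admission only. The short one needs perceived relatedness either way. It must also satisfy the rest of (b), that intervention was needed to avert one of the outcomes in (a).

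**3. Does another section bring it back?**
- 9.3.5, 24-hour rule: no, because the event is not life-threatening.
- 9.3.5, 72-hour rule: it applies to events already classed as SAEs, and step 2 has removed this one.
- 9.2.1: an investigator who is unsure must treat the event as related to the study drug. That does not help when the investigator is confident of another cause.
- 9.2.3: it has no relatedness condition of its own, but it refers back to 9.1.5.

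**4. Is it at least an AE?** Not necessarily. Section 9.1.1 also requires perceived relatedness, and its eCRF condition requires relatedness to the drug. Bullet 2 of 9.2.5 lets the investigator leave the event out if it looks like the underlying disease or is common in this population.

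**5. What the classification changes.**
- SAE: CIOMS form within 24 hours (9.3.2) and sponsor report within 72 hours (9.3.5).
- AE entered on the CRF: within 15 days, that is 15 × 24 = 360 hours, and 360 / 72 = 5 times the SAE limit.
- Neither: no record required.

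**The case against.** The strongest reply is that little is lost. Hemoglobin drops of 10 g/L or more are outcome 17. Transfusion, intravenous iron and anemia-related emergency visits are outcome 16, and Appendix C checks escalation at weeks 1, 4, 8 and 12. Sections 10.1 and 10.2 ask for a final visit, follow-up of unresolved AEs, and continued laboratory and quality-of-life data after withdrawal, although 5.4.2.2 and 10.0 end follow-up at escalation. Most of this stands for anemia. But a hospital admission as such is not on the escalation list, outcome 16 triggers no expedited report, and neither outcome is designed to capture admissions for other causes.

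A second reply is that 9.3.5 can be read as overriding (c), and that (c) itself is lenient, since a possible link to the arm is enough. Even so, the *prolonged* wording in (a) would remain. Sections 9.3.1 and 9.3.2 also invoke local and regulatory requirements that are not in these documents, so the text shows that a report can be missed, not that one will be.

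A reader might infer more in two ways. The first is that 9.2.5 leaves worsening anemia unrecorded. The documents do not establish this: bullet 1 deals specifically with a condition recorded at baseline that gets worse, and it plausibly prevails over the general bullet 2. The second is that the review cited in 2.1.5 (RR 1.26 for anemia on intermittent dosing) measures the harm at issue. It does not. It concerns women between menarche and menopause dosed three times a week or less, whereas alternate-day dosing averages 7 / 2 = 3.5 times. Its outcome is presence of anemia, not worsening or admission, and mean hemoglobin was similar (difference -0.15 g/L).

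**Conclusion.** The point holds as an internal conflict. Section 9.1.5 as written is narrower than 9.3.5, 9.2.4 and the CIOMS form, and a short, non-life-threatening admission judged unrelated can miss both the 24-hour form and the 72-hour report. Discretionary bullet 2 of 9.2.5 can then remove it from AE recording as well.

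The severity is minor, and the issue is safety reporting rather than analysis. The primary outcome and every planned estimate are unaffected. The documents give no admission rate, so no expected number of missed reports is claimed. The conclusion assumes that sites classify events by the protocol's own definitions and that the physician is confident of a cause outside the study.

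**What to change.** - **9.1.5.** In (a), write *requires inpatient hospitalization or prolongs an existing hospitalization*. Delete (c) and the *AND* before it. State that relatedness is assessed separately under 9.2.1, and that the closing paragraph, including its underlying-disease sentence, guides causality only and does not decide whether an event is an SAE.
- **9.1.1 and 9.2.5.** Add that the relatedness and underlying-disease exclusions, including bullet 2, do not apply to any event meeting the 9.1.5 seriousness criteria. Elective procedures stay excluded under bullet 3.
- **10.1.** Change the withdrawal reason to *serious adverse events judged related under 9.2.1*. Otherwise the wider definition would itself add withdrawals.

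A rule that any worsening of anemia or its symptoms must always be recorded is not needed. It has no threshold, so a 1 g/L fall would count.

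The cost is a protocol wording change and a few more SAE reports, each with a CIOMS form. No visit, blood test or questionnaire is added, because Appendix C already schedules AE and SAE assessment at all five follow-up contacts.

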9.3 Procedures for Reporting a Serious Adverse Event and Unanticipated Events

9.3.1 Investigator reporting: Notifying the REB

Serious adverse events and unanticipated events should be recorded and reported to the REB in accordance with local reporting requirements and timelines.

9.3.2 Investigator reporting: Notifying the Sponsor

The investigator is responsible for reporting SAEs and SUADRs to the sponsor (Sunnybrook Research Institute) in accordance with applicable regulations and reporting requirements and timelines.

Events that are assessed to be **serious and unexpected and related or cannot be ruled out as related** to the investigational product are considered SUADRs. Reporting for SUADRs should include a description of the event in sufficient detail to allow for a complete medical assessment of the case and independent determination of possible causality. The minimum information required includes at least one identifiable participant, one identifiable reporter, one serious reaction, and one suspect product.

Additionally, for SAEs and SUADRS, a Suspect Adverse Reaction Report – CIOMS I Form (see appendix D) must be completed by the investigator and forwarded to the Sponsor within 24 hours of site awareness.

Information on other possible causes of the event, such as concomitant medications and illnesses should also be provided as soon as is made available.

9.3.3 Sponsor Reporting of SUADRs: Notifying Health Canada

The regulatory sponsor is responsible for reporting SUADRs to regulatory authorities in accordance with local expedited reporting requirements and timelines. In addition, the Sponsor will complete the ADR Expedited Reporting Summary Form and submit this form in conjunction with the completed CIOMS Form to the appropriate Health Canada directorate.

9.3.4 Sponsor Reporting of SUADRs: Notifying Sites

The regulatory sponsor is responsible for distributing expedited reports of SUADRs to each investigator for submission to local Ethics Committees within 15 days of sponsor awareness.

9.3.5 Reporting and Entry Timelines

Study investigators will report SAEs to the sponsor within the following timelines:

- All deaths and immediately life-threatening events, whether related or unrelated, will be recorded and reported to the sponsor within 24 hours of site awareness.
- Serious adverse events other than death and immediately life-threatening events, regardless of relationship, will be reported to the sponsor within 72 hours of site awareness.

Adverse event information will be entered into the CRF in a timely manner and **no later than 15 days** from the time the investigator becomes aware of the event.

Serious adverse event information will be entered into the CRF in a timely manner/**within 72 hours** from the time the investigator becomes aware of the event.

9.4 Data and Safety Monitoring Board (DSMB)

A data and safety monitoring board is not deemed to be required because: 1) this is a pilot randomized trial to assess feasibility; 2) there are no concerns regarding unacceptable toxicity; 3) the experimental arm is the same drug but at a lower dose; 4) the primary outcome is not a “major endpoint” such as mortality; and 5) there are no ethical concerns regarding possible extreme efficacy of one arm so as to consider stopping the trial early.

10.0 CRITERIA FOR WITHDRAWAL AND DISCONTINUATION FROM STUDY

Patients will be followed until 12 weeks or until there is an escalation of therapy as defined by need for: alternative oral iron therapy (including if a participant in the every other day group escalates to daily iron), need for intravenous iron, need for transfusion, or a visit to emergency department related to anemia.

10.1 Early Termination and Reasons for Withdrawal

Patients may find that they are not able to continue in the study due to intolerable side effects from the oral iron despite simple measures to address the side effects. Patients are permitted to withdraw consent at any time if they desire and will not undergo further trial investigations if they do so.

Additionally, patients who become pregnant during the course of the study will be stopped from using the study medications and withdrawn from the study. Other reasons for withdrawal include use of

intravenous iron, use of blood transfusion, any deviation from inclusion/exclusion criteria and serious adverse events (as described in section 9.3).

Participants withdrawing from the study should be contacted by the study research team requesting a final visit and to follow up with any unresolved adverse events. Once withdrawn from the study, no further study procedures or evaluations should be performed, or additional study data collected. However, every effort should be made to obtain permission to document the reason for withdrawal and to collect participant outcomes, such as survival data up to the protocol-described end of participant follow up period, where possible. Any data collected prior to the withdrawal of consent may be retained and used by the sponsor. If the patient withdraws from the study, the research team will notify the patient's referring physician.

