5.2.2 Exclusion Criteria

- Pregnancy
- Currently breastfeeding
- Known history of inflammatory bowel disease
- Known history of celiac disease
- Known history of thalassemia or thalassemia trait
- Known inherited bleeding disorder

- Known intolerance or lack of response to oral ferrous gluconate, sulfate or fumarate in the last 12 weeks
- Multivitamin and mineral supplements (35 mg or more of elemental iron per day) in the 2 weeks prior to randomization
- Allergy to oral iron
- Allergy to any of the following medicinal and non-medicinal ingredients in ferrous sulfate: ferrous sulphate, calcium citrate, crospovidone, FD&C Red #40-Aluminum lake, FD&C Yellow #6-Aluminum Lake, magnesium stearate, microcrystalline cellulose, polyethylene glycol, polyvinyl alcohol, purified water, talc titanium dioxide
- Allergy to any of the following medicinal and non-medicinal ingredients in vitamin C: Ascorbic acid, Colloidal silicon dioxide, croscarmellose sodium, magnesium stearate, microcrystalline cellulose and stearic acid
- Intravenous iron therapy in the past 12 weeks
- On new anticoagulant therapy initiated in the past 6 months (e.g. warfarin, apixaban, dabigatran, edoxaban, rivaroxaban)
- Surgery planned in upcoming 12 weeks
- Chemotherapy planned in upcoming 12 weeks
- Blood donation planned in upcoming 12 weeks
- Previously enrolled in the study
- Creatinine clearance less than 30 mL/min
- Hemoglobin less than 80 g/L with active bleeding (defined as WHO grade 2 bleeding or higher in the past week)

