5.3.4 Adherence and Dose Modification

This is a pragmatic trial. Adherence will be documented by patients by providing a patient diary (see Supporting Documents) which shows the days on which they are supposed to take oral iron. This will be provided in a paper format. The research team will remind the patient to fill in their patient diary at 4 and 8 weeks. At the 12 week visit, the patient will be instructed to bring in their patient diary and pill bottle. A pill count will also be done to confirm adherence.

It is anticipated that ~ 30% of patients may not tolerate oral iron. The patient adherence diary instructions (see Supporting Documents) can be referred to for simple instructions (under point # 5) if the patient is having mild symptoms with the oral iron. Side effects may improve over the initial 1-2 weeks of oral iron. However, in some cases, patients may not be able to tolerate oral iron. Patients will be instructed to follow their planned schedule as prescribed. If they continue to have symptoms, patients will be instructed to step down in frequency (e.g. from daily to every other day; from every other day to two times per week; from two times per week to once per week) and to record how frequently they are able to take oral iron.

If patients are unable to take the oral iron at all, they will be continued to be followed as long as they are willing to continue and do not meet any criteria for withdrawal. Please refer to Section 10. Criteria for withdrawal from study.

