8.2 Final Analysis Plan

The results of this pilot trial will be used to assess the feasibility and inform the design of the definitive trial. We will present point estimates of feasibility events, including enrolment, adherence to protocol and accrual, as proportions with 95% confidence intervals. We will present continuous data as means and standard deviations, or medians and inter-quartile ranges, as appropriate.

An intention-to-treat analysis will be performed on all patients randomized for the secondary efficacy outcome. A per protocol analysis will be conducted for patients who have taken at least 90% of the

prescribed doses. Subgroup analysis will be performed on the stratified groups with hemoglobin 100g/L or greater and hemoglobin less than 100g/L. Additional subgroup analyses will include: patients with ongoing bleeding (WHO grade 2 or higher) vs no bleeding; and normal vs. increased CRP (based on the normal range).

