10.2 Data Collection and Follow-up for Withdrawn Participants

Patients will be asked to continue with follow-up quality of life assessment and laboratory tests. It is important to continue to follow these patients and capture outcomes that occur once they have discontinued study intervention to determine feasibility. Through telephone calls and emails, every effort will be made to obtain permission to document the reason participants withdrew consent and to continue collecting the quality of life assessments and laboratory values previously mentioned. Patients who have completed at least 90% of the prescribed doses will be included in the per-protocol analysis.

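### Sections 10.1 and 10.2 conflict on follow-up after withdrawal for an eligibility deviation, so week-12 hemoglobin can be lost from the intention-to-treat analysis in 8.2

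*Combined protocol and SAP*

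**What the plan says.** Section 10.1 adds to its reasons for leaving the study, after intravenous iron and transfusion, "any deviation from inclusion/exclusion criteria and serious adverse events (as described in section 9.3". The eligibility item carries no qualifier on when or how the deviation came about. Of patients withdrawn for any of these reasons it says: "Once withdrawn from the study, no further study procedures or evaluations should be performed, or additional study data collected". The next sentence softens this by asking for every effort to obtain permission "to collect participant outcomes, such as survival data up to the protocol-described end of participant follow up period, where possible".

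Section 10.2, whose heading covers withdrawn participants, says: "Patients will be asked to continue with follow-up quality of life assessment and laboratory tests". It gives as its reason that outcomes after stopping the study intervention matter for judging feasibility.

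Section 8.2 states: "An intention-to-treat analysis will be performed on all patients randomized for the secondary efficacy outcome". The Protocol Summary says the same of the secondary clinical outcomes. Section 8.2 names no method for missing values.

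Section 5.4.5 has its own route for deviations: document them, report them as required, and assess them in the analysis where necessary.

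**The concern.** Intention-to-treat needs outcome data on randomized patients whether or not they turn out to have met the entry criteria. Section 10.1 makes an eligibility deviation a reason to leave the study, not merely a fact to record, and joins it to a stop on data. Section 10.2 points the other way. Two sites could handle the same patient differently, and each could cite the protocol.

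The loss need not be neutral. Under 5.4.2.2 a patient whose hemoglobin has fallen by more than 10 g/L at week 4 goes back to the most responsible physician, and a reason for the fall is recorded. A patient being investigated is more likely than others to have a listed condition, or an overlooked entry fact, come to light. "Known history of celiac disease" is one such item in 5.2.2. Everyone knows the allocation, so the intensity of that search could differ between arms.

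At stake are the hemoglobin increment and the other secondary clinical outcomes, and the mean and SD of the increment that 8.1 wants from this pilot to size the definitive trial.

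**Working it through.** **1. The provisions side by side**

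| Section | Patient withdrawn for an eligibility deviation |
|---|---|
| 10.1, general rule | No further procedures or data |
| 10.1, exception | Outcomes sought with permission, where possible; survival is the only example |
| 10.2 | Asked to continue laboratory tests and quality of life; side effect questionnaire not mentioned |
| 5.4.5 | Deviation documented and assessed in analysis |
| 8.2 | In the intention-to-treat analysis if randomized |

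The first row cannot be followed together with the third, and following it leaves the last without week-12 data. Section 10.2 does not clearly settle the matter: its text speaks of patients who stopped the study intervention or withdrew consent, and does not mention eligibility.

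**2. Who is caught.** Section 5.3.1 confirms eligibility before randomization, so the clause must at least cover entry errors discovered later. Whether it also covers a condition first diagnosed on study is unclear. On a strict reading a diagnosis unknown at entry is not a deviation from a known-history criterion, but 10.1 does not say so.

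**3. The plan's own figure.** Inputs from 8.1, Table 2: margin 5 g/L, SD 5 g/L, true difference 0, one-sided 0.05, power 90%, drop-out 30%.

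- Per arm: 2 × SD² × (1.645 + 1.282)² / margin² = 2 × 25 × 8.567 / 25 = 17.1, rounded up to 18; total 36.
- With drop-out: 36 / 0.70 = 51.4, rounded up to 52.

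Both match the table.

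**4. Precision, for scale only.** The documents give no rate of ineligibility found after randomization. I assume 0 to 8 losses below 36. Power = Φ(5 / (SD × √(2/n)) − 1.645), with n per arm:

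| Analysed | SD 5 | SD 10 |
|---|---|---|
| 36 | 91.2% | 44.2% |
| 32 | 88.2% | 40.9% |
| 28 | 84.2% | 37.4% |

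These are scale markers. Section 8.2 sets no non-inferiority decision for the pilot, and 8.1 continues the trial until at least 36 patients complete. Further enrolment restores the count; it does not undo selective loss.

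**5. Bias.** If m of n patients in an arm are missing, and their mean increment is d below that of the patients observed, the observed arm mean is too high by (m/n) × d. The between-arm bias is the every-other-day value of this term minus the daily value, and is zero when the two are equal. The documents give neither m nor d. One patient carries a weight of 1/26 = 3.8% in an arm.

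**6. Why the SD matters.** Losing patients from the low tail also narrows the observed SD. In Table 2, at difference 0 and 90% power, the total is 36 at SD 5, 80 at SD 7.5 and 140 at SD 10. This shows how strongly the planning depends on the SD; it does not estimate what this clause would do to it.

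**7. The primary outcome.** Section 7.1 defines enrolment by documented consent, so withdrawal after randomization leaves time to enroll 52 unchanged.

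**The case against.** The strongest case against is that the protocol largely intends the right thing. Section 10.2 asks for the laboratory tests, 10.1 itself seeks some outcomes, and 5.4.5 already handles deviations in the analysis. Most data loss linked to poor response comes from other rules: assessments end at escalation of therapy (5.4.2.2, 10.0), and intravenous iron and transfusion are separate withdrawal triggers. The eligibility clause adds only patients found ineligible without escalation, who may be few. All of that stands. It limits the size of the problem but leaves 10.1 and 10.2 unreconciled.

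Some stronger readings should be resisted:

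- A reader might infer that failing to respond, or becoming intolerant, on study makes a patient ineligible. The criterion in 5.2.2 concerns known intolerance or lack of response before entry. If entry criteria applied continuously, the hemoglobin and ferritin limits would withdraw responders too. Section 10.1 lists on-study pregnancy and intravenous iron separately, which would be largely redundant on that reading. Section 5.3.4 also says "If patients are unable to take the oral iron at all, they will be continued to be followed as long as they are willing", provided no withdrawal criterion is met.
- A reader might infer that data collection certainly ends. The documents conflict on this.
- A reader might infer that withdrawn patients are removed from the intention-to-treat set. Nothing in 8.2 does so, and data collected before consent is withdrawn may be kept. The likely effect is missing later values with no stated handling.
- A reader might size the tilt by assuming a few zero-gain patients lost from one arm and comparing the shift with the 5 g/L margin. Every input would be assumed, and a one-arm shift is not a between-arm shift unless the other arm has no comparable losses.

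**Conclusion.** The concern holds as a conflict between sections that can cause avoidable data loss. A site following 10.1 would lose later hemoglobin values, chiefly at week 12, for randomized patients found ineligible afterwards, although 10.2 asks for those values and 8.2 relies on them. That the loss is related to response or arm is plausible from 5.4.2.2 and the open-label design, but the documents do not show it. The size cannot be derived: there is no rate, and the precision figures rest on an assumed 0 to 8 further losses. The effect falls on the secondary clinical outcomes and on the increment mean and SD carried into the definitive trial. This should be corrected, but it does not undermine the trial's feasibility aim.

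**What to change.** Reconcile 10.1 with 10.2 along these lines:

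> A randomized patient later found to deviate from an eligibility criterion is recorded as a protocol deviation (5.4.5). This finding alone does not end data collection. Unless consent is withdrawn, the week 4 and week 12 laboratory tests and the scheduled questionnaires continue.

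Add to 8.2:

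> Such patients are analysed in the arm to which they were randomized. Any analysis leaving them out is a sensitivity analysis, limited to facts that existed before randomization.

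The last limit matters because facts arising later can depend on response or on how hard each arm was investigated. Section 8.2 should also say how any values still missing are handled.

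The change governs data collection and analysis only. Section 10.1 does not separate stopping study drug from leaving the study, so the sponsor should state what happens to treatment; nothing is proposed here on that.

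The cost is one short amendment. The downside is that a few patients who did not meet the criteria stay in the intention-to-treat set.
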